5.3. Response Evaluable Analysis Set

The response evaluable set is defined as patients who have received at least one cycle of study treatment unless discontinued early due to death or PD and have had at least one disease assessment following the initiation of therapy. A subject completes a cycle if the daily treatment compliance of napabucasin/amcasertib/sorafenib for Arm1/Arm2/Arm3 respectively is 80% or higher in that cycle (cycle 1 or cycle 2). The response evaluable set will be used for analyses of DCR and ORR, as a sensitivity analysis to ITT analysis.

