#### 10 PLANNED STATISTICAL METHODS

# 10.1 Analysis Populations

The study populations for subsequent analyses below will be defined for phase Ib, phase II, and overall.

Enrolled Patients: A patient is considered enrolled upon receiving the first dose of

sorafenib on Cycle 1, Day 1.

Study Drug Safety Population: Defined by all patients receiving at least one dose of study drug

(either BBI608 or BBI503).

Pharmacokinetic Population: Defined as those patients who have completed all pharmacokinetic

assessments.

Dose-Escalation Population: Patients are considered evaluable for the determination of dose-

escalation if they:

a) Experience dose-limiting toxicity (DLT)

b) Complete 28-days of combination dosing at the assigned

dose-level

Population Evaluable for

Response:

The evaluable population is those patients who have received at least one cycle of study drug (either BBI608 or BBI503) and who have had at least one objective disease assessment following the

initiation of therapy.

Intent to Treat Population: All randomized patients, regardless of receiving a dose of

sorafenib or study drug.

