Medical history will be coded using the Medical Dictionary for Regulatory Activities (MedDRA[®]) v19.0. Medical history will be summarized by system organ class (SOC) and preferred term (PT) using the number and percentage of patients for the ITT analysis set.

Duration of Overall Survival (OS) Follow-up

The duration of overall survival (OS) follow-up is defined as time from the date of randomization to either death or the last known visit alive. The median follow-up time for OS and the corresponding 95% confidence interval (using the method of Brookmeyer and Crowley, 1982 with the log-log transformation) will be summarized using the reverse Kaplan-Meier (KM) method for the safety set. The analysis involves the event and censoring rules to be switched (i.e., the patients who die become ‘censored’, and the censored patients are treated as the ‘event’).

Summaries of the number and percentage of patients who have died, those still in survival follow-up, those lost to follow-up, and those who have withdrawn consent will be also provided.

Extent of Exposure

Exposure may be summarized (per cycle and/or overall) as dose received (cumulative dose or actual dose intensity) or as dose received relative to the intended dose (relative dose [RD], or relative dose intensity [RDI]), or both.

The information that will be summarized depends on how the study drug is dosed (e.g., infusion cyclical, oral daily, oral cyclical).

Actual treatment duration = actual end of treatment date – date of first dose of study drug + 1

- For napabucasin, amcasertib, and sorafenib, the actual end of treatment date is the last dosing date

Cumulative dose in a cycle or overall is the sum of the actual doses received in a cycle or overall, respectively.

Intended cumulative dose in a cycle or overall is the sum of the intended dose level doses in a cycle or overall, respectively.

Actual Dose Intensity [DI]

- By cycle actual DI (*dose unit/day*) = [cumulative dose in the cycle] / [actual cycle duration in days]
- Overall actual DI (*dose unit/day*) = [overall cumulative dose] / [actual treatment duration in days]

Relative Dose Intensity (RDI): The basic intent is to evaluate dose per *time unit* factoring in dose reductions, interruptions, or delays.

Relative dose intensity (RDI) by cycle and overall:

- Intended DI (*dose unit/day*) = [intended cumulative dose per cycle] / [intended number of days in a cycle]
- By cycle RDI (%) = $100 \times$ [by cycle actual DI] / [intended DI]

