- Overall RDI (%) = $100 \times$ [overall actual DI] / [intended DI]

Daily treatment compliance

Daily treatment compliance will be reported for each patient by phase, treatment arm and dose level cohort.

- The % of days the patient received full daily dose of napabucasin/amcasertib or sorafenib or higher out of actual treatment duration in days.
- The % of days the patient received a non-zero dose of napabucasin/amcasertib or sorafenib out of actual treatment duration in days.

Daily treatment compliance will be grouped according to the following categories: < 60%, ≥ 60% - < 80%, ≥ 80% - < 90%, ≥ 90%, and will be summarized for all arms.

These summaries will be performed for cycle 1 and overall.

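### SAP 5.3 judges cycle completion by a compliance measure whose denominator ends at the last dose, so read literally a patient who stops after a few gap-free days has completed a cycle

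*SAP*

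**What the plan says.** SAP 5.3 requires one cycle of study treatment and at least one disease assessment after therapy starts. Patients who stop early because of death or PD are excused the cycle condition. Receipt of a cycle is decided by compliance: "A subject completes a cycle if the daily treatment compliance of napabucasin/amcasertib/sorafenib for Arm1/Arm2/Arm3 respectively is 80% or higher in that cycle". Either of the first two cycles may qualify: "is 80% or higher in that cycle (cycle 1 or cycle 2").

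SAP 7.2.1 gives the only definition of daily treatment compliance, in two versions. One is "The % of days the patient received full daily dose of napabucasin/amcasertib or sorafenib or higher out of actual treatment duration in days"; the other is "The % of days the patient received a non-zero dose of napabucasin/amcasertib or sorafenib out of actual treatment duration in days". Both share a denominator: "Actual treatment duration = actual end of treatment date – date of first dose of study drug + 1", and "For napabucasin, amcasertib, and sorafenib, the actual end of treatment date is the last dosing date". On the periods covered, the section says "These summaries will be performed for cycle 1 and overall".

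Protocol 10.1 describes the evaluable population as patients who have "received at least one cycle of study drug (either BBI608 or BBI503") and who have had a disease assessment. It gives no compliance formula.

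SAP 5.3 and 7.2.2 use the set as a sensitivity analysis for ORR and DCR, which SAP 2.1 names as the phase II primary endpoints. Table 2 in SAP 7.2.3.2 also lists the set for PFS.

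**The concern.** A rule meant to show that a cycle was received should fail someone who took only a small part of one. Here the denominator shrinks with the numerator: once dosing stops for good, no further days are counted. The 80% threshold then measures gaps before the stop, and length of treatment drops out.

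At stake is what the sensitivity analysis means. It is there to show whether the ITT response rates hold up among patients who actually received a cycle. If a few days of dosing can qualify, it does not answer that question. Section 5.3 also does not choose between the full-dose and non-zero-dose measures, and it needs a cycle 2 value that 7.2.1 does not list. Two programmers could therefore build different sets from the same data.

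**Working it through.** **Inputs.** The threshold is 80%, in cycle 1 or cycle 2 (SAP 5.3). Cycles are 28 days, and napabucasin or amcasertib starts on Cycle 1 Day 15 (SAP 1.1), so cycle 1 holds 28 − 14 = 14 planned days of either drug. The target is 30 patients in each of Arms 1 and 3 (Protocol 10.3). The plan states no figure that depends on this rule, so there is none to reproduce.

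**Step 1: the rule as defined.** Compliance = 100 × dosed days / (last dosing date − first dose date + 1). Take an illustrative Arm 1 patient who receives full-dose napabucasin on Cycle 1 Days 15, 16 and 17 and then stops permanently for toxicity: 100 × 3 / (17 − 15 + 1) = 3/3 = 100%. The full-dose and non-zero-dose measures agree here. The threshold is met. One day would do as well: 1/1 = 100%.

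**Step 2: the same patient against planned days.**

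| Denominator | Compliance | 80% rule |
|---|---|---|
| First to last dose (SAP 7.2.1) | 3/3 = 100% | passes |
| Planned napabucasin days in cycle 1 | 3/14 = 21.4% | fails |
| Full 28-day cycle | 3/28 = 10.7% | fails |

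On planned days, passing takes at least 12 of 14 days (85.7%; 11/14 = 78.6% fails) or 23 of 28 (82.1%; 22/28 = 78.6% fails).

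**Step 3: can this patient reach the set?** Yes, with one later scan. Protocol 5.7.2 continues imaging every 8 weeks after treatment stops, until progression by both criteria. Protocol 7.1 says the same for Arm 3 patients who stop sorafenib.

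**Step 4: is this what the plan intends?** Three places suggest not.
- SAP 5.3 excuses early stops for death or PD. That is needed only if early stoppers otherwise fail. With the last-dose denominator, a gap-free early stopper passes anyway, so the exemption has little left to do.
- Protocol 7.4 calculates compliance against the number of capsules or tablets due, and Protocol 4.6 requires both 28 days of exposure and 80% compliance for DLT evaluability. SAP 5.3 keeps the 80% and has no duration condition.
- Protocol 11.3 refers to four weeks of study drug when it discusses who is not evaluable for response.

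**Step 5: size.** One patient is 1/30 = 3.3% of an arm. The documents give no rate of early stopping. If 5% to 20% of an arm stopped within a cycle for reasons other than death or PD (an assumption), that would be 0.05 × 30 = 1.5 to 0.20 × 30 = 6 patients. This is an upper range: some would have gaps that take them below 80%, and some would never be scanned.

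**The case against.** The best reply is that SAP 5.3 asks for compliance in a given cycle, while actual treatment duration describes the whole course of treatment. SAP 7.2.1 separates the two levels for dose intensity, using actual cycle duration by cycle and treatment duration overall. On a cycle-length reading the three-day patient scores 10.7% or 21.4%. If duration is counted from the first sorafenib dose on Day 1, the score is 3/17 = 17.6%. All of these fail, and the problem disappears.

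This stands in part: the literal reading is not the only possible one. But the cycle-duration denominator is given for dose intensity alone. The compliance definition is tied to actual treatment duration even though its summaries include cycle 1. The alternative has to be borrowed, so 5.3 needs an edit on either reading.

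The limits on impact stand in full. There is no hypothesis testing, the set serves a sensitivity analysis, and for PFS the text of 7.2.3.2 specifies ITT while only Table 2 adds this set.

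Two stronger readings are tempting, and the documents support neither.
- A reader might infer that the rule also wrongly drops patients who pause and resume. A patient dosed on 22 of 28 days with the last dose on Day 28 scores 78.6% now, and the same on planned days. That is the threshold at work, not the denominator, and such a patient can still qualify through the other cycle.
- A reader might infer that the compliance table is wrong. It is stated as a percentage of actual treatment duration, which is a valid on-treatment measure. Early stopping is reported elsewhere, through discontinuation reasons, treatment duration and adverse events leading to discontinuation.

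**Conclusion.** The concern holds in a limited form. Under the only definition the SAP gives, a patient who takes treatment without gaps for a few days and then stops for a reason other than death or PD scores 100% and meets the cycle-completion rule. That contradicts the requirement of at least one cycle in both documents. If scanned afterwards, the patient is counted in the response-evaluable set.

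The effect is confined to the ORR/DCR sensitivity analysis and to PFS where Table 2 uses the set. The ITT results do not change. Each such patient is 3.3% of a 30-patient arm; 1.5 to 6 per arm is only an assumed upper range. The documents do not settle the direction of any effect on the response rates. The conclusion rests on applying the compliance definition in 7.2.1 to 5.3 as written. A team that silently used cycle length would avoid the problem, but the SAP does not tell it to.

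**What to change.** In SAP 5.3, define per-cycle compliance as dosed days divided by the planned dosing days of that cycle: 28, or 14 for napabucasin and amcasertib in cycle 1 if cycle 1 stays a qualifying cycle. Whether to keep it should be a deliberate choice, because 12 study-drug days would then count as a cycle. Count days after a permanent stop as not taken, and keep the existing exemption for death or PD.

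State in 5.3 whether the full-dose or the non-zero-dose measure applies. This can change membership, because sorafenib dose modification is allowed. Derive the measure for cycle 2 as well as cycle 1. Label the compliance table in 7.2.1 as on-treatment, so that it is not read as completion of planned treatment.

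The cost is a few words in two SAP sections and one changed denominator in programming. The downside is that a few early stoppers leave a sensitivity set.

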5.4. Dose Escalation Evaluable Analysis Set of Phase Ib

Patients are considered evaluable for the determination of dose escalation if they:

- a) Experience a DLT
- b) Complete 28 days of combination dosing at the assigned dose level

6. DATA HANDLING

6.1.1. Methods for Handling Missing Dates

For patient data listings, no imputation of incomplete dates will be applied. The listings will present incomplete dates, if applicable, without any change.

Missing or Partial Death Dates

Completely missing death dates will be imputed as the day after the date of last contact.

A death date missing the month and day will be imputed as Jan 1st of the year or the date after the date of last contact, whichever comes last.

A death date missing the day will be imputed as the 1st of the month or the day after the date of last contact, whichever comes last.

Date of Last Dose of Study Drug

No imputation will be done for first dose date. No imputation will be done for the date of last dose for patients off study. The date of last dose will be imputed by the analysis cutoff date for ongoing patients.

Date of Start of New Anti-Cancer Therapy

Incomplete dates for the start date of new anti-cancer therapy will be imputed as follows and will be used for determining censoring dates for efficacy analyses:

- Completely missing start date will be imputed as the day after study failure/relapse/PD, or the end date of new anti-cancer therapy if available, whichever comes first
- Start date missing both the month and day will be imputed as Dec 31st of the year, or the end date of new anti-cancer therapy if available, whichever comes first
- Start date missing the day will be imputed as the last date of the month, or the end date of new anti-cancer therapy if available, whichever comes first

Missing Dates in Adverse Events/Concomitant Therapies

Every effort will be made to avoid missing/partial dates in on-study data. Start dates of AEs/concomitant therapies will be imputed as follows:

- Completely missing start date will not be imputed.

Start date missing both the month and day will be imputed as:

- The date of the first dose if the year of the start date is the same as the date of first dose;
- otherwise, Jan 1st of the year of the start date will be used.

Start date missing the day will be imputed as:

- The date of first dose if the year and month of the start date are the same as the date of first dose;
- otherwise, the 1st of the month of the start date will be used.

Stop dates of AEs/concomitant therapies will be imputed as follows:

- Completely missing stop date will not be imputed.

- Stop date missing both the month and day will be imputed as Dec 31st of the year of stop date.
- Stop date missing the day will be imputed as the last date of the month of the stop date.

After imputation, the imputed date will be compared against the date of death, if available. If the planned imputed date is later than the date of death, the date of death will be used as the imputed date instead.

Missing Dates in Prior Therapies

Dates missing the day or both the day and month of the year will adhere to the following conventions:

- The missing day of start or end date of prior therapy will be imputed as:
 - the 15th of the month or date of informed consent, whichever is earlier.
- If the start or end date of a prior therapy is missing both the day and month, the date will be imputed as:
 - July 1 of the year or date of informed consent, whichever is earlier.
- If date is completely missing, then no imputation will be done.

6.2. Definition of Baseline Values

- Efficacy: The last measurement on or prior to the date of randomization will serve as the baseline measurement. In the event such a value is missing, the last assessment completed prior to the first study drug administration will be used as the baseline assessment.
- Safety: The last measurement prior to the first study drug administration will be used as the baseline assessment.

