## **5.3** Pre-Study Evaluations (Baseline)

After written informed consent is obtained according to ICH-GCP and local regulations, the patient will be evaluated for inclusion and exclusion criteria according to the eligibility criteria listed in Section 3.

The Pre-Study evaluation may be held up to 5 days ( $\pm 2$ ) prior to the first dose of sorafenib and/or study drug (either BBI608 or BBI503). The following evaluations will be obtained (unless otherwise obtained as a part of standard of care).

- Medical history, including resolved medical/surgical conditions, active concurrent medical conditions/adverse events, concurrent medications, as well as detailed history of current cancer diagnosis, treatment, and response to treatment (see Section 6.1).
- Vital signs (weight, temperature, blood pressure, height, respiration and pulse) and Physical examination, including documentation and measurement of any external or palpable subcutaneous lesions (see Sections 9.1.2 and 9.1.3)
- ECOG performance status (see Section 16)
- Hematology (see Section 6.3)
- Blood chemistry (see Section 6.3):
- Urinalysis (see Section 6.3)
- Serum pregnancy test (if applicable)
- Serum AFP level\* (see Section 6.3)
- Electrocardiogram\*
- Assess Child Pugh Class
- Optional tumor biopsy, if applicable\* (see Section 6.5.2)
- Tumor lesion measurement and staging according to RECIST 1.1 as well as modified RECIST for patients with HCC [computed tomography (CT) of the chest, abdomen, and pelvis with tri-phasic liver scan *or* magnetic resonance imaging (MRI) of the abdomen and pelvis with contrast plus a CT scan of the chest without contrast in case of allergic reaction to CT scan contrast despite appropriate pre-treatment] \*\*

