#### 6 STUDY PROCEDURES

# **6.1** Medical History

A complete medical history will be obtained. The components will include, but are not limited to, the following:

- Demography: date of birth, sex, race, ethnicity, height, and weight
- Clinically significant prior non-cancer diagnoses, surgeries, and current medications
- Prior cancer history, current cancer diagnosis, tumor stage at time of diagnosis and at time of study screening
- Prior surgical procedure(s), including date, anatomic site, and specific procedure performed; including loco-regional liver-directed therapy such as embolization, chemoembolization, radiofrequency ablation, etc.
- Current and prior modifiable risk-factors (smoking, alcohol use, including estimated amount and duration of use)
- Prior imaging reports, lesion measurements, and/or image reproductions may be requested from different periods in the cancer-specific history for a given patient.
- The suspected causal setting in which HCC arose is requested (i.e., a history of hepatitis C (HCV), hepatitis B (HBV), or inherited metabolic disorders).
- History of non-alcoholic fatty liver disease (NAFLD), if any
- Smoking and tobacco history
- In addition to AFP levels at baseline, at least one alfa-feto protein (AFP) level from before the baseline visit is requested, in order to establish two AFP levels prior to starting sorafenib on study.

Prior records, radiology reports, or procedure notes may be required in order to verify components of study patient history.

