The phase II portion is an open-label, 3-arm, randomized phase II trial of patients with advanced HCC who have not received prior systemic treatment. Patients will be randomized to receive either Arm 1: sorafenib administered in combination with napabucasin (at the RP2D determined for napabucasin plus sorafenib during the phase Ib portion); Arm 2: sorafenib in combination with amcasertib (at the RP2D determined for amcasertib plus sorafenib during the phase Ib portion), or Arm 3: sorafenib alone at a starting dose of 400 mg twice daily. The starting dose for sorafenib is the same for all study arms.

When protocol amendment 3 [2] is in effect, Arm 2 in the Phase II portion was closed for enrollment due to amcasertib portfolio priorities and to increase efforts in enrolling patients to Arms 1 and 3.

At the time amendment 3 was in effect, there were approximately 10 patients already enrolled in Arm 2. Therefore, the actual sample size in Phase II by the end of the study is projected to be approximately 70 patients after amendment 3. Protocol therapy will continue in repeating 28-day cycles until disease progression, unacceptable toxicity, or another discontinuation criterion is met. Pharmacodynamic assessments will be performed in patients with readily accessible tumors through an optional on-study tumor biopsy. Archival tissue, if available, will be collected from all patients. Throughout the study, safety and tolerability of napabucasin in combination with sorafenib and of amcasertib in combination with sorafenib will be assessed for the duration of study treatment and up to 30 days after discontinuation of study drug (either napabucasin or amcasertib).

Evaluation of anti-tumor activity will be performed at regular 8-week intervals, with the first assessment 8 weeks (56 days) after Cycle 1, Day 1. The radiologic assessments will be evaluated according to response evaluation criteria in solid tumors (RECIST) 1.1 and modified RECIST (mRECIST) for patients with HCC. Alpha-feto protein (AFP) measurements will be performed at baseline, at the end of the 2-week sorafenib monotherapy Run-In, and at the start of each subsequent study cycle.

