7.2.4.1. Adverse Events

Overall Summary of AEs

An AE will be regarded as **treatment-emergent**, if:

- it occurs on the day of or after the first dose of napabucasin or amcasertib or a combination drug and up to 30 days after the last dose of any study drug; or
- it occurs prior to first dose date of napabucasin or amcasertib or a combination drug and worsens in severity on therapy and up to 30 days after the last dose of study drug.

Adverse events will be coded by SOC and PT using the MedDRA v19.0. The severity of AEs will be graded by the investigator using (NIH NCI CTCAE Version 4.0). The verbatim term will be included in the AE listings.

An overview of treatment-emergent adverse events (TEAEs) will be provided. The number and percentage of patients will be summarized for:

- Patients with at least one TEAE
- Patients with TEAEs of CTCAE Grade 3 or higher
- Patients with serious TEAEs
- Patients with napabucasin-related TEAEs

- Patients with napabucasin-related TEAEs of CTCAE Grade 3 or higher
- Patients with amcasertib-related TEAEs
- Patients with amcasertib-related TEAEs of CTCAE Grade 3 or higher
- Patients with sorafenib-related TEAEs
- Patients with sorafenib-related TEAEs of CTCAE Grade 3 or higher
- Patients with napabucasin-related serious TEAEs
- Patients with napabucasin-related serious TEAEs of CTCAE Grade 3 or higher
- Patients with amcasertib-related serious TEAEs
- Patients with amcasertib-related serious TEAEs of CTCAE Grade 3 or higher
- Patients with sorafenib-related serious TEAEs
- Patients with sorafenib-related serious TEAEs of CTCAE Grade 3 or higher
- Patients with TEAEs leading to napabucasin dose hold
- Patients with TEAEs leading to dose reduction of napabucasin
- Patients with TEAEs leading to amcasertib dose hold
- Patients with TEAEs leading to dose reduction of amcasertib
- Patients with TEAEs leading to sorafenib dose hold
- Patients with TEAEs leading to dose reduction of sorafenib

Summary of AEs during Run-in Period

Besides overall summary of AEs as described above, the analysis of AEs during Run-in period will be summarized separately. Run-in Period is defined from the first sorafenib dose date to one day prior to patient administrated the napabucasin/amcasertib, or to the end of treatment if patient discontinued the study treatment before the napabucasin/amcasertib administration. For Phase II sorafenib monotherapy arm patients, run-in period is defined as the first 14 days of sorafenib administration.

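### Does the undefined term 'study drug' in SAP 6.2 leave the safety baseline open to falling after the sorafenib run-in?

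*SAP*

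**What the plan says.** The safety bullet of SAP 6.2 reads: "The last measurement prior to the first study drug administration will be used as the baseline assessment". The efficacy bullet above it uses randomization as its reference and falls back on the same undefined event when no value exists by then.

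Some passages keep sorafenib out of the term:
- Protocol 5.3 names the two separately: the pre-study visit is held "prior to the first dose of sorafenib and/or study drug (either BBI608 or BBI503").
- Protocol 10.1 describes its Study Drug Safety Population thus: "Defined by all patients receiving at least one dose of study drug", with BBI608 and BBI503 as the only drugs listed.
- SAP 1.1 says safety is followed "up to 30 days after discontinuation of study drug (either napabucasin or amcasertib").

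Other passages in the SAP include sorafenib:
- SAP 7.2.1 measures treatment duration from the first dose of study drug and then specifies: "For napabucasin, amcasertib, and sorafenib, the actual end of treatment date is the last dosing date".
- SAP 7.2.4.1 opens the treatment-emergent window at the first dose of either agent or a combination drug and closes it "up to 30 days after the last dose of any study drug".

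**The concern.** Sorafenib is given alone from Cycle 1 Day 1, and the combination starts on Day 15. Protocol 5.4.3 schedules laboratory tests, vital signs and an ECG on Day 15 before the first BBI608 or BBI503 dose, and says these values show what sorafenib alone has done. If study drug excludes sorafenib, the Day 15 values become the baseline in the combination arms. Arm 3 (sorafenib alone) and patients who stop during the run-in would have no anchor.

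The awkward case is a repair made in Arm 3 only. If sorafenib were substituted there and nowhere else, run-in changes still present on Day 15 would count as post-baseline change in the control arm and be absorbed into baseline in Arms 1 and 2. Safety and tolerability are part of the phase II primary objective, so a tilt of this kind in the shift and maximum-change tables would matter to a reader comparing arms.

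**Working it through.** No figure in the plan is in dispute. The check is which reading the rest of the plan can support.

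**1. Distance between the candidate anchors.** Day 15 minus Day 1 is 14 days.

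**2. Test of the reading without sorafenib.** Protocol 10.3 gives phase II sizes of 30 (Arm 1), about 10 (Arm 2) and 30 (Arm 3), so the total is 30 + 10 + 30 = 70. Arm 3 never receives napabucasin or amcasertib, so 30/70 = 42.9% would have no safety baseline. SAP 5.2 puts anyone who took sorafenib into the safety set and uses that set for laboratory tests and vital signs. SAP 7.2.4.2 requires baseline values and maximum change by treatment arm in that set. This reading makes a required table impossible for one whole arm.

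**3. Test of the reading with sorafenib.** It fits the SAP's analysis rules:
- the safety set (5.2) admits patients on sorafenib only;
- the exposure rule (7.2.1) covers all three drugs;
- the treatment-emergent rule (7.2.4.1) opens with a combination drug. The SAP also tabulates treatment-emergent events within the run-in, counted from the first sorafenib dose and including the first 14 days of Arm 3. That table makes sense only if sorafenib starts the clock.

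It also fits what the documents call baseline. SAP 1.1 lists two separate time points: "Alpha-feto protein (AFP) measurements will be performed at baseline, at the end of the 2-week sorafenib monotherapy Run-In". Protocol 6.1 asks for an additional AFP value from before the baseline visit "in order to establish two AFP levels prior to starting sorafenib on study". Protocol 5.3 labels the pre-study visit as baseline, 5.7.1 dates baseline imaging from the first sorafenib dose, and 6.5.2 places the baseline biopsy before sorafenib.

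**4. What a split baseline would do, if anyone used one.** No passage states it. The counts below come from Protocol Appendix B. They give scheduled post-baseline assessments with a pre-sorafenib baseline (Arm 3) against a Day 15 baseline (Arms 1 and 2).

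| Measure | Arm 3 | Arms 1 and 2 |
|---|---|---|
| Hematology and chemistry through Day 1 of cycle c | 1 + (c − 1) = c | c − 1 |
| same, c = 3 | 3 | 2 |
| same, c = 6 | 6 | 5 |
| Vital signs through Cycle 3 Day 1 | 5 (6 if the Day 8 contact is in person) | 4 |
| ECG | 2 | 1 |

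The vital-sign row assumes that Cycle 1 Day 1 readings precede the first sorafenib dose. The ECG row assumes that Arm 3 has a Day 15 ECG. Appendix B marks that visit, but its footnote ties the ECG to a BBI608 dose, and 5.4.3 says only that laboratory tests remain required in Arm 3. Protocol 5.5.2 also lets the Cycle 2 Day 15 ECG move to a later visit. With sorafenib counted as study drug, every row is equal across arms and the difference is zero.

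**5. Reach.** The safety rule feeds the laboratory shift and maximum-change tables, the ECG shift table and the vital-sign change table (SAP 7.2.4.2 to 7.2.4.4). Treatment-emergent events and the Grade 3 proportion do not use it. The efficacy fallback shares the phrase but should seldom apply, because Protocol 4.3 requires screening to be complete before randomization is requested.

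**The case for a change.** The strongest case for a change runs as follows. SAP 1 says it is to be read with the protocol, and the protocol repeatedly ties study drug to BBI608 or BBI503. A programmer who applies that meaning is following the documents. SAP 5.3 already uses a different drug in each arm to define a completed cycle, so an arm-by-arm baseline is conceivable. A run-in laboratory abnormality could then be treatment-emergent in the adverse-event table and missing from the shift table. SAP 7.2.1 has an explicit anchor for medications, the first of napabucasin or backbone, and 6.2 could have used it. The cost is one line.

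The wording point stands: 6.2 leaves the term undefined, the efficacy fallback repeats it, and the medication anchor itself omits amcasertib. The harm does not follow. The narrow wording in SAP 1.1 sits in the design summary, not in an analysis rule. The SAP replaced the protocol's Study Drug Safety Population with a wider set. The protocol is not strict either: Appendix B, which covers Arm 3, times the End of Study visit from the last dose of study drug, where 5.1 says protocol therapy. The cycle-completion rule in SAP 5.3 serves the response evaluable set and says nothing about baseline. The mismatch between adverse-event and shift tables is itself a reason for analysts not to use a Day 15 baseline.

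**Conclusion.** No change to the plan follows. SAP 6.2 leaves a detail unstated, and the surrounding sections supply it: the last value before the first dose of any protocol therapy, which in every arm means before sorafenib. On that reading all arms share the same baseline point and no table is tilted. The 43% describes an implementation that the SAP's own by-arm tables rule out, and the unequal counts describe a convention that no passage states. A clarifying sentence would be harmless, but it would only write down what analysts would very likely do.

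This rests on two assumptions. First, whoever programs the tables reads 6.2 together with SAP 5.2, 7.2.1 and 7.2.4. Second, the eCRF visit labels, which SAP 6.3 relies on and which are not available here, do not designate Day 15 as baseline. If a split baseline were used after all, its effect on the tables could not be estimated from the documents. It would be confined to descriptive safety tables in a study with no hypothesis test (SAP 3.1).
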